9.2 Sample Size and Randomization

In **Table 8** below we present a range of minimum detectable effect size differences for the primary outcomes of Pain Interference or Function Scores for both the administrative sample (N=84 per clinic) and survey sample (N=42 per clinic) for 16 clinics (8 clinics randomized to each arm) for Aim 1. Sample size calculations for the cluster randomized design were based on the net difference between the two conditions across baseline and 3-months follow-up.⁵⁰ We assumed over time correlations of 0.50 for both patients (based on data from the [name] et al. pilot study³³ and summary data available for Durham VA clinics, intraclass correlation coefficients (ICC) of 0.01, 0.02, and 0.05 to account for clinic clustering, and also adjusted for the potential group-level randomization of up to 4 stratification variables as baseline covariate adjustments where we conservatively assumed no reduction in either group or subject level variance components. For all calculations, the type-I error is 2.5% to account for the multiple primary outcomes and power is conservatively assumed to be 90% to guard against deviations from assumptions. The number needed at baseline (N_b) is based on an attrition rate of 20%. Note in the **below Table 4** that the scenarios above lead to having adequate power to detect a medium effect size for the primary outcomes for both the administrative and survey samples.

Table 8. Minimum detectable effect size differences for 90% power, alpha of 0.025 and ICC of 0.01, 0.02, and 0.05 for administrative outcome (n=84 per clinic) and survey outcome (n=42 per clinic)

Number of clinics per condition	Number of patients per clinic needed at post-intervention follow-up (Total N)	Minimum Detectable Effect Size Difference ICC=0.01	Minimum Detectable Effect Size Difference ICC=0.02	Minimum Detectable Effect Size Difference ICC=0.05	Number of patients per clinic needed at baseline with 20% attrition (Total N_b)
8	42 (N=672)	0.37	0.42	0.55	53 (N_b =848)
8	84 (N=1344)	0.30	0.36	0.50	105 (N_b =1680)

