In planning for the UH3, we have determined that we cannot roll out the interventions for all 16 clinics at the same time due to logistical constraints. Therefore, we plan to conduct a covariate constrained randomization in 2 blocks following the extension to randomize multiple blocks of groups by Carter and Hood.⁵⁴ In the first block we will have 10 clinics and the second block will have 8 clinics if no clinics drop out of block 1 before randomization occurs in the second block. The second block will include 2 reserve clinics for use if a clinic should drop out from block 2 (see Section 8). In the standard covariate constrained randomization all participating clusters need to be enrolled before randomization. We are concerned that clinics that would roll out later in the schedule may lose interest or drop out if we enroll and randomize all clinics at once at the beginning of the study. An advantage of the blocked compared to the standard randomization is that, if a clinic would drop out in the first block before we randomize the second block, we would

be able to add clinics in the second block to compensate for the loss. As we cannot roll out the interventions at all clinics at the same time within a block, following randomization, we will then randomly pair one ICP clinic and one CCP clinic and then randomly order pairs for intervention roll out and recruitment.

As this is a cluster randomized embedded pragmatic trial, patients, intervention delivery personnel and recruitment personnel will not be blinded to clinic intervention assignment. However, research personnel collecting study surveys by telephone will be blinded.

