9.5 Outcomes

9.5.1 Primary Outcome

Co-primary outcomes will be pain interference with normal activities and functional status, assessed by PROMIS Short Form scores collected in the EHR on the administrative sample (n=1680) at baseline and 3 months; 3 months is the primary outcome time point. For baseline and 3-month follow-up, we will rely on central delivery personnel and clinical providers in ICP and pain navigators in CCP to collect these data in the EHR via progress note templates to collect health factors relevant for the analysis for the PROMIS pain interference and functions scores (see Section 6). For the follow-up, a report will be generated every 2-weeks to evaluate which participants are due for the 3-month follow-up and the report will be sent to central delivery personnel or pain navigator for them to administer these measures (see outcome ascertainment study flow diagram in Figure 4. The window around the 3-month outcome assessment will be 1-month. If outcome assessment occurs outside of this defined window they will not be included in the primary analysis. Given that this is an embedded pragmatic trial the study team will monitor outcome ascertainment timing at each participating clinical site to trouble-shoot any problems or issues to circumvent loss of outcome data.

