9.6 Data Analyses

Aim 1 Analyses

The primary outcomes are continuous and will be ascertained at the planned baseline and follow-up assessment (3 months) from administrative data collected from the EHR on all eligible LBP Veterans presenting at participating clinics. Changes in pain interference and/or physical function scores will be estimated and the primary hypotheses tested via hierarchical linear mixed-effects models with patients nested within clinics and baseline and 3 month values in the response vector.⁵⁵ Hierarchical linear models are a flexible and powerful analytic tool for clustered longitudinal continuous outcomes. The fixed-effect portion of the model will have the form: $Y_{ijk} = \beta_0 + \beta_1 * (followup) + \beta_2 * (followup * intervention)$ for clinic i , patient j , at time k . Random effects (clinics and time by clinics) will be included in the model to account for clustering of patients within clinics as the clinics are the unit of randomization, random effects will also be included to account for the within-patient correlation between repeated measures over time. We will assess the best fitting random effects structure by fitting a variety of random coefficient models (e.g., random intercept only, random intercept and linear slope) and assess using Akaike Information Criteria (AIC) model selection criteria.^{56,57} The predictors in the model will include a time effect and indicator variables for treatment interacting with the time effect. The intraclass correlation capturing the relationship of outcomes between patients seen at the same clinic is accounted for via the random effects for the clinics and time by clinics, which are assumed to be normally distributed. The model will be fit in the SAS procedure PROC MIXED using full likelihood approximation and the hypotheses will be tested by whether the estimated coefficient β_2 is positive and significantly different than 0 at the 0.025 level due to 2 primary outcome variables. We will include covariates used in the covariate constrained randomization⁴ (5 potential variables; average pain scores, clinic location (main medical center/community clinic), number of participating primary care providers, average level of opioid exposure of LBP patients at clinic, and average age of LBP patients at clinic) in our primary model as well as a limited number of patient-level covariates that are readily available in the EHR (age, gender, race and a comorbidity measure). While we have procedures in place to monitor timing of the 3-month follow-up assessment in the EHR, if we have a significant number of assessments outside the 1-month window for the 3-month assessment that are dropped from the primary analysis, we will conduct a sensitivity analysis including the assessments outside the window and estimating a 3-month treatment effect from this model.

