
Secondary Analyses

We will assess differences in proportions of “responders” between treatment arms for each of the primary outcomes. A “responder” will be defined as achieving 30% improvement in pain interference or function scores at 3 months follow up.⁵⁸ Responder status for those missing outcome data will be estimated using best linear unbiased predictors from the hierarchical linear model⁵⁹ so that those missing observed follow up data will be included.

We will use a generalized linear mixed model with a logit link function to compare differences in responder status between arms where the main predictor of interest will be treatment arm adjusting for clustering of VA clinic either with random effects or by conditioning.^{55,60,61} As a sensitivity analysis to explore responder cut points of pain interference and function measures, we will compute cumulative proportion responder analysis graphs.⁶²

Secondary outcomes of sleep, opioid use, and health utilization (including chronic opioid usage) will also be obtained administratively on all eligible subjects. The sleep PROMIS measure is a continuous outcome that will be assessed at baseline and 3 months and similar modeling procedures as described for the primary outcomes will be used. Opioid use will be examined in two ways, one as a binary variable based on whether a chronic opioid user or not at baseline and 12 months and second using a continuous measure of morphine equivalents for opioid dose at baseline and 12 months.⁶³ For the dichotomous outcomes, we will use a generalized linear mixed model with a logit link function where the main predictor of interest will be treatment arm and will include baseline opioid use status (chronic or not chronic) adjusting for clustering of VA clinic either with random effects or by conditioning.^{55,60,61} For opioid morphine equivalent dose, we will fit a similar model as was described for the primary outcomes except the follow up time point in the model will be for 12 months. For imaging and ED utilization, we will assume a count-like distribution for the number of ED visits in the 12 months of follow up and will use generalized linear mixed model for count variables.⁵⁵

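### The responder model omits the patient's own baseline PROMIS score, which costs roughly 11 to 20 points of power for physical function and almost none for pain interference

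*Combined protocol and SAP*

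**What the plan says.** Section 9.6 (Secondary Analyses) has a responder "defined as achieving 30% improvement in pain interference or function scores at 3 months follow up". A generalised linear mixed model with a logit link will then "compare differences in responder status between arms where the main predictor of interest will be treatment arm adjusting for clustering of VA clinic", by random effects or by conditioning. No other term is named. Baseline enters only through the responder definition and, for patients without follow-up, through the linear-model predictions used to fill in their status. The one sensitivity analysis stated for responders, the cumulative-proportion graphs, varies the cut point only.

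Two neighbouring models do deal with baseline. The binary opioid model in the same section "will include baseline opioid use status (chronic or not chronic) adjusting for clustering of VA clinic". The primary model in 9.6 has "baseline and 3 month values in the response vector" and no arm main effect, so both arms share a baseline mean. The patient-level covariates listed for that primary model are age, gender, race and comorbidity. Carrying that list over to the responder model would not bring in a PROMIS baseline.

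Section 9.5.1 has both PROMIS scores collected in the EHR on the administrative sample "at baseline and 3 months; 3 months is the primary outcome time point". The covariate is therefore already in hand.

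**The concern.** Whether a patient counts as a responder depends partly on where that patient started. For function, someone who starts low needs fewer points to gain 30% and also tends to regress upwards. A model with only arm and clinic leaves this predictable patient-level variation in the error, so the comparison is weaker than the collected data allow.

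There is a second, conditional issue. If the arms differ at baseline by chance, regression to the mean alone can produce a difference in responder proportions. The secondary result could then disagree with the primary model, which constrains the baseline means, for a reason unrelated to the pathways.

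**Working it through.** **Inputs from the documents.** Sections 9.2 and 9.3: 16 clinics (8 per arm), 84 patients per clinic at follow-up, ICC 0.01, 0.02 and 0.05, and two-sided 0.05 for secondary analyses. On correlation, 9.2 says "We assumed over time correlations of 0.50". Section 9.2 gives detectable effects of 0.30 to 0.50 SD, mapped to 2.4 to 5.0 points of pain interference, which implies an SD of 2.4/0.30 = 8 to 5.0/0.50 = 10.

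**Assumptions not in the documents.** Baseline mean 38 for function and 62 for pain interference; SD 8 to 10 applied to function as well; control-arm change of 0 to 0.4 SD; some effects below 0.30 SD; complete cases. The documents state no power or responder rate for this analysis.

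**The plan's own figure first.** The detectable effect in Table 8 is (t[0.9875, df] + t[0.90, df]) × sqrt(4(1 − r)(1 + (m − 1)ICC)/(m g)), with r = 0.5, m = 84, g = 8 and df = 2(8 − 1) − 5 = 9.
- The t-values are 2.685 + 1.383 = 4.068.
- ICC 0.01: 4.068 × sqrt(2 × 1.83/672) = 0.300.
- ICC 0.02: 0.362. ICC 0.05: 0.504.

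Table 8 gives 0.30, 0.36 and 0.50, so the design inputs reproduce.

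**How far response depends on baseline.** Let Y0 and Y1 be the baseline and 3-month scores, with equal SDs and correlation 0.5.
- Function responds when Y1 − 1.3·Y0 ≥ 0. Its correlation with Y0 is (0.5 − 1.3)/sqrt(1 + 1.69 − 1.3) = −0.8/sqrt(1.39) = −0.68, so R² = 0.46.
- Pain interference responds when Y1 − 0.7·Y0 ≤ 0. The correlation is (0.5 − 0.7)/sqrt(1 + 0.49 − 0.7) = −0.2/sqrt(0.79) = −0.23, so R² = 0.05. It is zero if the over-time correlation is 0.7.

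These values do not depend on the assumed means. They already show that the point concerns function.

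**Power.** A random-intercept logistic model (t-test on 14 df) was fitted to simulated trials without and with the patient's baseline score, 500 to 1,000 runs per case.

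| Outcome, SD, control change (points) | Effect (SD) | ICC | Without | With |
|---|---|---|---|---|
| Function, 8, 0 | 0.30 | 0.01 | 70.6% | 82.4% |
| Function, 8, 3.2 | 0.25 | 0.01 | 62.1% | 79.2% |
| Function, 10, 4 | 0.30 | 0.02 | 71.9% | 89.2% |
| Function, 8, 0 | 0.36 | 0.02 | 80.4% | 91.2% |
| Function, 8, 0 | 0.50 | 0.05 | 85.0% | 97.4% |
| Pain interference, 8, 3.2 | 0.30 | 0.01 | 45.4% | 44.0% |
| Pain interference, 10, 4 | 0.30 | 0.01 | 77.0% | 78.0% |

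The gain for function is about 11 to 17 points. A two-stage analysis of clinic-level residuals gives 11 to 20. For pain interference it is −1 to +2 points.

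**Baseline imbalance, no treatment effect** (function, 30% rule, ICC 0.01).
- No imbalance imposed: unadjusted false-positive rate 4.4%.
- 0.2 SD imbalance that regresses to a common mean (follow-up shift = 0.5 × 0.2 SD): false difference about 3.5 points, with rejection 26.7% unadjusted and 4.5% adjusted.
- 0.2 SD deficit in the integrated pathway that persists at follow-up: unadjusted +1.0 to +1.5 points with rejection about 8 to 10%; adjusted −1.7 to −2.3 points with rejection about 15 to 17%.

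The chance SD of the baseline arm difference is sqrt(2(1 + 83·ICC)/672) = 0.074, 0.089 and 0.124 SD at the three ICCs. At ICC 0.01, 0.2 SD is therefore 0.2/0.074 = 2.7 chance SDs.

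**The case against.** A reader might infer that any baseline difference between arms becomes a false responder difference, and that adding the baseline score cures it. Section 9.2.1 seems to invite this, since it says "patients, intervention delivery personnel and recruitment personnel will not be blinded to clinic intervention assignment" and patients enter by referral after the clinics are randomised. The documents do not support that reading, for four reasons.

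- It barely applies to pain interference. With imposed imbalances of 0.1 and 0.2 SD, the false difference was 0.1 to 0.5 point and the false-positive rate about 4 to 5%.
- Without an imposed imbalance the unadjusted test keeps its level. The documents give no figure for referral imbalance. They also describe constrained randomisation on clinic averages (9.2.1), training in the referral criteria (4.1), and treating providers with no knowledge of the comparison pathway (6.3).
- Under Tables 4 and 5 and section 9.3, baseline PROMIS is first recorded at the initial pathway contact, after referral. Referral on underlying severity could leave a deficit at both times. Adjustment then gives a larger error in the opposite direction, as the last case above shows.
- The omission is by silence. Calling arm the main predictor leaves room for other covariates.

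All four stand. They remove the claim of a general bias and the claim of a cure. They do not touch the precision argument for function. On silence, the opioid sentence shows that the plan names a baseline term where one is intended, and 6.3 says the statisticians are unblinded, so the choice is better fixed in advance.

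**Conclusion.** The point holds as one of precision, for physical function. At a correlation of 0.50 under the 30% rule, omitting the baseline score costs roughly 11 to 20 points of power (11 to 17 with the mixed model itself). The size rests on the assumed mean near 38 and SD of 8 to 10; the direction follows from the latent correlation of −0.68, which needs neither. For pain interference the loss is negligible.

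The bias argument holds only for a chance imbalance in function that regresses to a common mean. It does not extend to lasting differences in who is referred. This is a secondary analysis, and the primary mixed model is unaffected. The change should be made, but the trial's main conclusion does not depend on it.

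**What to change.** In 9.6, Secondary Analyses, state that each responder model includes the patient's baseline score on that PROMIS scale as a continuous covariate, in parallel with the opioid model, which "will include baseline opioid use status (chronic or not chronic"). Report a model-standardised difference in responder proportions beside the odds ratio. The unadjusted result can stay as a sensitivity analysis. Do not describe the adjustment as protection against differential referral.

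The cost is one or two sentences and a variable already collected in the EHR. The small downside is that the odds ratio becomes conditional on baseline; the standardised difference guards against misreading it.

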6.3 Blinding

Blinding

Given the pragmatic design, participants and treating providers will not be blinded to the care pathway. **Table 6** below summarizes blinding status for various study team members and also treating providers. Treating providers delivering the clinical pathways at a clinic and the Veteran patients in that pathway have no knowledge or training on the comparison pathway being delivered at other clinics as part of this study. Treating providers entering health factor data in the EHR will not be blinded. However, survey outcome assessors (RA conducting telephone

surveys) will be blinded to care pathway received. Study statisticians cannot be blinded to clinic randomization arm as they will be monitoring data collected in the EHR to track study flow, provide feedback to clinics and identify barriers or problems. Because the data entered in the EHR is different due to the nature of each of the interventions, it is not possible for study statisticians to be blinded in the conduct of this study. Study statisticians will be generating the randomization tables using a covariate constrained randomization and provide a report to inform clinics of their randomization arm.

Table 6. Blinding Summary for AIM-Back Trial

Study personnel	Clinic level randomization blinding status	Clinic level blinding status justification	Individual patient level data access	Individual patient level data access notes
PIs	Unblinded	Site recruitment and engagement role, troubleshooting barriers to clinical intervention delivery of programs; management of centralized intervention delivery	No	Access to aggregated patient data presented in reports for tracking and troubleshooting
Research coordinator	Unblinded	Site recruitment and engagement and monitoring of delivery of clinical intervention	No	Access to aggregated patient data presented in reports for tracking and troubleshooting
VA research assistant	Blinded		Yes	Administering patient surveys
DCRI research assistants	Blinded		Yes	Administering patient surveys
PhD Statistician	Unblinded	Involved in monitoring data in EHR including assessing targeted sample size goals; conducting and verifying covariate constrained randomization	Yes	Access intermittently to troubleshoot any problems with recruitment, data collection and data quality

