The survey outcomes for the enrolled subset of patients will be collected at baseline, 3, 6, 9, and 12 months and will include pain interference, function, intensity, catastrophizing, sleep, and depression (see Section 10 for full descriptions). These are all longitudinal continuous outcomes and a hierarchical linear model similar to that described for the primary aim will be fit. We will fit random coefficient models as described above (e.g. random intercept only, random intercept and linear slope) and assess using AIC model selection criteria to determine best model for the covariance structure. Similarly, we will determine the best model for the mean structure (e.g. linear, quadratic, dummy coding) as there are five outcome measurement occasions guided by descriptive plots and model fit assessed using AIC model selection criteria. Due to the timing of administration of baseline surveys that some baseline surveys may occur after the initial intervention contact, we will conduct sensitivity analysis treating baseline surveys after initial provider contact as occurring in the post-treatment period.

Aim 2 Analyses

As highlighted in the UG3 section we have strong clinical and scientific rationale to investigate chronic vs. acute LBP and previous opioid use vs. opioid naïve as *a priori* subgroups for treatment moderation.³⁸ We will define “chronic low back” as pain that has persisted for at least 3 months and resulted in pain on at least half the days in the past six months to be consistent with the NIH task force definition.⁴⁹ All participants will have chronicity of back pain assessed via the EHR template (see Section 6) at the time of initial referral to a given care pathway using questions specified in the NIH minimum dataset.⁴⁹ Opioid exposure prior to pathway entry will be defined as being prescribed at least one prescription opioid for 20 or more consecutive days (yes or no within 12 months prior to entering pathway).⁶⁴ This definition could be altered if different ones are suggested for use by the PMC3. These data will be obtained through VA’s Pharmacy Benefits Management System.

For the planned subgroup analyses for key moderators on the primary outcomes of pain interference and function will be the same modeling framework as described for AIM 1 with the addition of the indicator variable(s) for the moderator and associated interactions.⁶⁵ The fixed-effect portion of the model will have the form: $Y_{ijk} = \beta_0 +$

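### The time form for the survey outcomes is chosen by plots and AIC on the data being tested, so the survey contrast is not fixed, and the survey 3-month effect can be understated with too narrow an interval

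*Combined protocol and SAP*

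**What the plan says.** Section 9.6 (Secondary Analyses) of the combined protocol and SAP covers the telephone-survey outcomes: pain intensity and interference, physical function, sleep, depression and catastrophizing. It states that "The survey outcomes for the enrolled subset of patients will be collected at baseline, 3, 6, 9, and 12 months" and that a model like the Aim 1 model will be fitted. Two parts of that model are left to the data. For the random part, the statisticians will "assess using AIC model selection criteria to determine best model for the covariance structure". For the fixed part, "we will determine the best model for the mean structure (e.g. linear, quadratic, dummy coding) as there are five outcome measurement occasions", a choice "guided by descriptive plots and model fit assessed using AIC model selection criteria".

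The Aim 1 model in the same section is handled differently. It is a model "with patients nested within clinics and baseline and 3 month values in the response vector", its fixed part is written out in advance, and AIC is used only for the random effects.

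On timing, Section 9.5.1 says of the co-primary EHR outcomes that "3 months is the primary outcome time point". The calculations in Section 9.2, which include the survey sample, "were based on the net difference between the two conditions across baseline and 3-months follow-up". A 3-month survey contrast is therefore implied, but no section declares one. No section gives a default time form or an allowance for having selected it. Section 6.3 adds: "Study statisticians cannot be blinded to clinic randomization arm as they will be monitoring data collected in the EHR".

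**The concern.** In a model of the Aim 1 type, the arm effect is the interaction of arm with time. The form chosen for time therefore defines the tested quantity: one slope difference under a line, two curve terms under a quadratic, or four visit differences under dummy coding. If that form is picked from the outcome data and then treated as fixed, the data decide what is tested, and the usual standard errors ignore the selection. Different outcomes could also end up tested on different contrasts.

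AIC rewards fit over the whole 12 months. It can drop terms that contribute little overall but carry most of the information about one visit. The visit most exposed is 3 months, which is the trial's main time point and the basis of the survey power calculation. The survey also matters in its own right. Under Section 6.3 its assessors are blinded while the providers entering EHR data are not, and under Table 10 it is the only source of PROMIS scores after 3 months.

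**Working it through.** **Inputs from the documents.** Section 9.2 gives 8 clinics per arm, 42 survey patients per clinic at follow-up, an over-time correlation of 0.50, ICCs of 0.01, 0.02 and 0.05, alpha 0.025, 90% power and 20% attrition. Section 9.6 gives the occasions 0, 3, 6, 9 and 12 months. Section 9.2.1 lists five randomization covariates. Section 9.3 makes tests two-sided.

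**Step 1: reproduce the plan's survey figure.** The net-difference formula is MDES = (t[0.9875, df] + t[0.90, df]) × √(4 × [(1−ICC)(1−0.5) + m × ICC × (1−0.5)] / (m × g)), with m = 42, g = 8 and df = 2(8−1) − 5 = 9. The t values are 2.685 + 1.383 = 4.068.

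- ICC 0.01: √(4 × 0.705 / 336) = 0.0916; × 4.068 = 0.373
- ICC 0.02: √(4 × 0.910 / 336) = 0.1041; × 4.068 = 0.423
- ICC 0.05: √(4 × 1.525 / 336) = 0.1347; × 4.068 = 0.548

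Table 8 prints 0.37, 0.42 and 0.55, so the design inputs are understood. At baseline, 42/0.8 rounds up to 53 per clinic, and 53 × 16 = 848, as stated.

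**Step 2: what each form does to a sustained effect.** Take an arm difference of 1 at each of 3, 6, 9 and 12 months (t = 1 to 4) and zero at baseline. Fit it by least squares through zero.

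- Line: slope = Σt/Σt² = 10/30 = 0.333. Fitted values are 0.33, 0.67, 1.00 and 1.33.
- Quadratic: solve 30a + 100b = 10 and 100a + 354b = 30. The determinant is 620, a = 540/620 = 0.871 and b = −100/620 = −0.161. Fitted values are 0.71, 1.10, 1.16 and 0.90.
- Dummy coding: 1.00 at every visit.

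So if chosen, a line reports 33% of the 3-month effect and a quadratic 71%. Full AIC fits weight the visits differently, so this shows direction and rough size only.

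**Step 3: how often a smooth form wins, and at what cost.** The simulation used 16 clinics of 42 completers, five occasions, the documents' ICCs and over-time correlation, a common baseline, and ML fits of all three forms. The lowest AIC was kept, with a naive 95% t interval (14 df) and 500 trials per case. The time profiles are assumptions. Results for the 3-month arm difference at ICC 0.02 with a flat or exactly linear shared course (equivalent, since every candidate form contains a line):

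| True arm effect | Smooth form wins | Bias toward zero (SD) | Coverage, AIC choice |
|---|---|---|---|
| Sustained 0.20 SD | line 24%, quadratic 52% | 0.052 | 65.6% |
| Sustained 0.42 SD | quadratic 30% | 0.030 | 73.0% |
| 0.42 SD decaying to 0 | quadratic 9% | 0.013 | 85.2% |
| Null, or linear to 0.42 SD | line 82%, quadratic 12% | about 0 | 93.6% |

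Dummy coding fixed in advance gave bias 0.003 SD, coverage 92.8% and half-width 0.18 SD in every row. In the first row the selected half-width averaged 0.109 SD.

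Within selected runs the effect is sharper. For the 0.20 SD effect, when a line wins the bias is 0.152 SD and coverage 0%. For the 0.42 SD effect, when a quadratic wins the bias is 0.139 SD and coverage 28.9%. Section 9.2 maps 0.37–0.55 SD to 3.0–5.5 points, that is 3.0/0.37 = 8.1 to 5.5/0.55 = 10 points per SD, so 0.139 SD is about 1.1 to 1.4 points. At ICC 0.01 and 0.05, coverage for the sustained 0.20 SD effect is 71% and 52%.

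**Step 4: vary the shared course (ICC 0.01–0.02, sustained effect).**

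- Flat: about 65–80% across implementations.
- 0.1 SD, or gradual from 0.15 to 0.3 SD: about 84–92% for effects of 0.2–0.4 SD, against 96–97% for dummy coding. Another implementation gave 81–85% against 94–95% for effects of 0.2–0.3 SD, so the figure is good to a few points only.
- Plateau of 0.2 SD: 90–94% in one implementation; about 95% in another with effects of 0.37–0.42 SD.
- Plateau of 0.3 SD: 94–96%.
- Plateau of 0.5 SD: dummy coding wins 97–100% of runs for sustained effects, and the result equals the dummy result.

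**Step 5: other quantities.** Coverage at 12 months stayed at 92–98%. Type I error at 3 months was 6.4% with selection against 7.2% with dummy coding in one implementation, 6.5–9.1% against 4.8–6.1% in a second, and about 7% against 4% in a third. That is not a consistent inflation.

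**The case against.** The strongest reply has five parts.

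1. **Role.** The Précis places these survey data in secondary and exploratory analyses, and the primary model has only two time points. This stands in full.
2. **Dummy coding is already a candidate, and plots would show a step at 3 months.** This stands in part. Plot judgement cannot be simulated and might rescue some cases. It is also the least reproducible part of the rule, and plots of 16 clinics are noisy.
3. **The harm rests on an assumed course.** The ICP runs 2 + 6 + 6 weeks, and Section 2.4 has the navigator's calls spread over 3 months. Both arms may therefore improve early, and an early shared improvement pushes AIC to dummy coding. This stands as a limit on the size. But the same timing makes an arm difference that is present by 3 months and then held a natural shape, and the sponsor cannot know the shared course in advance for each outcome.
4. **Categorical time costs precision.** At ICC 0.02 the 3-month half-width is 0.18 SD against 0.043 when a line is chosen. If the course is truly linear, that is a real loss.
5. **A 3-month difference can be computed from any form.** True, but the plan does not say that this will be the reported quantity.

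Several stronger readings are tempting and not supported. A reader might infer that any smooth form biases the 3-month effect, but under a null or linear effect the chosen line is unbiased with 97% coverage. A reader might take the 133% at 12 months in Step 2 as the expected error there, but 12-month coverage is close to nominal. Section 6.3 might suggest that unblinded statisticians will steer the choice, but it gives EHR monitoring as the reason for unblinding and says nothing of the kind.

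**Conclusion.** The concern holds in a limited form. Section 9.6 lets the tested data choose the time form, and with it the survey contrast, and nothing elsewhere fixes either. The survey 3-month estimate is pulled toward zero, with an over-narrow interval, when two things coincide: a smooth form is selected, and the true arm effect is not of that form. The loss of coverage is material when the shared course is flat, moderate when shared improvement is small or gradual, and negligible once there is a clear early shared improvement.

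These sizes depend on assumed profiles, complete balanced data, one covariance structure and no covariates. With 500 trials per case, the error on overall coverage is about 1 to 2 points. They also represent AIC alone. Type I inflation is not established, and the co-primary EHR result is untouched. This is a worthwhile, cheap improvement to a secondary analysis and does not threaten the trial's main conclusion.

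**What to change.** In the survey paragraph of Section 9.6:

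- State that time is categorical at each outcome's scheduled occasions, with arm-by-occasion terms: 3, 6, 9 and 12 months in general, and 3 and 12 months for the PHQ-2, which Table 10 collects only at baseline, 3 and 12 months.
- Name the 3-month and 12-month arm differences as the reported survey contrasts.
- Keep linear or quadratic curves as description or sensitivity analysis.
- AIC may still guide the covariance structure, as in the Aim 1 model.

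The cost is SAP wording and a few parameters. Four time and four arm-by-time terms replace one of each under a line, so at most 8 − 2 = 6 are added, with 672 patients expected at follow-up. The other cost is a wider 3-month interval if the true course is linear. For the PHQ-2 a quadratic already fits both follow-up visits exactly, so there the change matters only against a line.
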